## Screening Instrument

ATN focus groups intake	
1. Initials	
2. DOB	
3. Age	
4. Gender Identity and Sexual Identity (MSM, Transwomen)	
5. Employment status?	
6. Eligible?	 Yes  No
7. Notes	

## APPENDIX III

### Planned Enrollment Report – Pilot Test

**This report format should NOT be used for collecting data from study participants.**

**Study Title:** Work-to-Prevent: Employment as HIV prevention for young men who have sex with men (YMSM) and young transgender women (YTW) [Pilot Test (n=70)]

**Domestic/Foreign:** Domestic

**Comments:** We define male to include anyone who was assigned male at birth, which would include young transgender women (YTW)

Racial Categories	Ethnic Categories				Total	
	Not Hispanic or Latino		Hispanic or Latino			
	Female	Male	Female	Male		
American Indian/ Alaska Native	0	0	0	0	0	
Asian	0	0	0	0	0	
Native Hawaiian or Other Pacific Islander	0	0	0	0	0	
Black or African American	0	48	0	4	52	
White	0	0	0	12	12	
More Than One Race	0	4	0	2	6	
Total	0	52	0	18	70	

## APPENDIX IV

### iFOUR Description

#### Description of the iFOUR Program

The Increase Individual Income and Independence program (iFOUR) is an employment program that was developed over ten years ago to target the employment needs of HIV-positive people. The program was based on the Supported Employment framework that was developed to help connect people with a range of disabilities (physical and cognitive) to employment because of the benefits of employment, both monetary and non-monetary. Thus, researchers at the University of Illinois-Chicago collaborated with Chicago House, a housing and support organization for HIV-positive individuals, to develop a Supported Employment program for HIV-positive individuals. Like Supported Employment, iFOUR provides a variety of supports to aid in participants' job success, such as job training referrals, client-tailored job placement, post-employment assistance, and benefits planning. The program includes regular interviews to evaluate program outcomes, such as medication adherence, use of drugs and alcohol, and assessments of physical and mental health. Since 2005, the iFOUR program has been refined to better tailor to the needs of HIV-positive individuals, including the addition of one-on-one work with a career specialist. These specialists assess job readiness and are trained in the impact of HIV/AIDS on employment, so as to best assist participants with their career aspirations. They also assist with linking participants to additional educational resources and provide support with interview preparation and development of resumes and cover letters. iFOUR also includes a four-week training workshop that is tailored to the needs of HIV-positive participants, dealing with questions such as workplace discrimination, benefits maintenance, and the relationship of health beliefs and work. The workshop also covers confidence and communication skills, while highlighting the non-monetary benefits of employment. The iFOUR program has had positive outcomes for participants, documented in several studies (see references below). The goal of the current study is to tailor and then pilot test the iFOUR program for individuals who are HIV-negative but at high-risk for acquiring HIV.

T3	Follow-up at 8-months (± 4 weeks) post-intervention
VDA	Values-Driven Attitudes
W2P	Work2Prevent
YMSM	Young Men who have Sex with Men
YTW	Young Transgender Women

1. INTRODUCTION

Work2Prevent (W2P) is a project designed to adapt, tailor, and pilot-test a novel social and structural-level HIV intervention for Young Men who have Sex with Men (YMSM) and Young Transgender Women (YTW) of color aimed at increasing economic stability (i.e., employment) through youth empowerment and asset development, and decreasing HIV risk behaviors (i.e., sex work) associated with social and economic marginalization. This document gives details of the planned statistical analysis for Phase 2 of the intervention.

1.1. Objectives and Research Hypotheses

The primary objective of Phase 2 is to pilot-test the intervention among up to 70 at-risk YMSM and YTW of color in order to evaluate feasibility and acceptability. Investigators hypothesize the intervention will increase job self-efficacy and readiness, as well as decrease HIV risk behaviors and STI and HIV infections.

2. STUDY METHODS

2.1. Study Design

W2P is a single-arm longitudinal pre and post study of the social and structural-level employment intervention to evaluate feasibility, acceptability, and satisfaction of the intervention program, and preliminary efficacy for study outcomes assessed at Baseline (T1), Post-Intervention (T2, 0 to 2 weeks post workshop completion), and 8-Month Follow-up (± 4 weeks) (T3). The study employment intervention is comprised of four structured workshops presented over a 2-week period.

The study aims to enroll up to 70 at-risk YMSM and YTW of color over a 6-month period. The intervention workshops will be completed within 12 weeks of enrollment. Each participant will then be assessed 8-months (± 4 weeks) post-intervention.

Study outcomes include: (1) Job self-efficacy and readiness; (2) HIV risk behaviors; (3) Employment; and (4) STI and HIV infections.

2.2. Study Population

All intervention study participants are Black or African American or Hispanic or Latinos males, including transgender women (those assigned male at birth), ages 16-24, who identify as either an (1) MSM or gay or bisexual man or as a (2) transgender woman or transsexual male-to-female or transwoman.

Participant Inclusion Criteria¹:

1. Being male or assigned male at birth (YTW)
2. Identifying as YMSM or gay bisexual man or transgender woman or transwoman
3. Identifying as African American or Black, Hispanic or Latino, or as a racial or ethnic minority or person of color
4. 16-24 years old
5. English-speaking (primary)
6. HIV negative or of unknown status
7. Currently unemployed but seeking employment, or employed only part-time (average of 35 hours or less per week)
8. Able to attend a 4-session employment program

Participant Exclusion Criteria:

1. Individuals identifying as non-Hispanic white
2. Individuals not assigned male at birth

2.3. Sample Size Information

This study aims to enroll up to 70 participants with at least 50 of these participants completing the study (~70% retention rate). Given the exploratory nature of this study and limited access to this population, a power calculation was not performed. A repeated measures design was chosen to reduce the variability in the estimate of the treatment effect, at the expense of having a comparison group. In addition, practice or fatigue effects from repetition may affect certain outcomes (e.g. protean career attitudes scale and subscales). This trade-off was appropriate given the exploratory nature of a pilot study and the limited access to the study population.

3. ANALYSIS POPULATIONS

Only participants who are enrolled at Baseline (complete the T1 survey) will be included in the primary and secondary analyses. Screen-failures will not be included in these analyses.

3.1. Intent-to-Treat Population

All participants who completed T3 will be included in intent-to-treat analyses involving variables measuring changes from T1 to T3 (see sections 4.1.3-4.1.4 and 4.2.1-4.2.5 below).

All participants who completed at least one workshop will be included in intent-to-treat analyses involving workshop evaluation and workshop completion variables (see sections 4.1.1,

¹ The original inclusion criteria included "Considered 'at-risk' for HIV based on 6-item risk assessment". The removal of this criterion was approved on August 16, 2018 as part of protocol v4.0 and eligibility was rerun retrospectively for those who completed the Screener Survey (SCR) prior to the inclusion criteria modification.

4.1.2 below). This population will form the basis for both the primary and secondary analyses of the efficacy and safety endpoints.

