## 6.3 Workshop Intervention

After the Baseline visit (T1), participants have up to 12 weeks to complete workshop classes for Phase 2 and up to 4 weeks for Phase 3, otherwise they will go on to complete the T2 and T3 visits. Participants who do not complete any workshop classes may still complete the T3 visit.

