3.2. Per Protocol Population

Youth who attend at least two of the four planned intervention workshops and complete T3 will comprise the per protocol population. This population will form the basis for both the primary and secondary supportive analyses of the efficacy and safety endpoints.

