4.1.2. Workshop Completion (T2)

Workshop completion will be used to assess for intervention feasibility. The outcome of intervention completion will be defined as having attended at least two of the four workshop sessions and will be measured by tracking participant attendance. Workshop completion may also be defined as the number of workshop sessions attended for use in exploratory analyses.

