1.2. WORKSHOP COMPLETION

Workshop completion will be used in the assessment of intervention feasibility. The primary outcome for workshop completion will be measured using a binary outcome of Complete vs. Not Complete (1.2.2), but the number of completed workshops (1.2.1) is also defined to assess potential dose response of the workshop intervention on other outcomes.

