1.2.1. Number of Workshops Attended

Description: The participants' workshop attendance is recorded in items 3a, 3c, 4a, 4c, 5a, 5c, 6a, and 6c of the Workshop Tracking Information (WTI) form.

Variable: WSATTEND_T2_1

Label: Number of Workshops Attended at T2

Type: Numeric; Range = 0 to 4

Algorithm: WSATTEND_T2_1 = SUM (WTI3a, WTI3c, WTI4a, WTI4c, WTI5a, WTI5c, WTI6a, WTI6c)

If all responses are missing, then WSATTEND_T2_1=Missing. Otherwise, sum non-missing responses. Note: WTI#c can only have a response if WTI#a=0.

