1.2.2. Workshop Completion

Description: Workshop completion is defined as having attended at least two of the four workshop sessions (50% completion).

Variable: WSCOMP_T2_1

Label: Workshop Completion at T2

Type: Numeric; Format: 0=Not Complete, 1=Complete, .=Missing

Algorithm: If WSATTEND_T2_1 >= 2 then WSCOMP_T2_1 = 1
Else if WSATTEND_T2_1 in (0, 1) then WSCOMP_T2_1=0
Else WSCOMP_T2_1 = .

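### Workshop completion, the primary feasibility outcome, is analysed only among participants who attended at least one workshop, so enrolled participants who attend none drop out of its denominator

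*SAP*

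**What the plan says.** The wording cited here is the same in the Phase 2 and Phase 3 SAPs.

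- **Role of the outcome.** Section 4.1.2 states: "Workshop completion will be used to assess for intervention feasibility". It defines completion as attending two or more of the four sessions, and section 5.4 lists it among the primary outcomes. Section 1.1 gives feasibility and acceptability as the primary objective of each phase.
- **Population.** Section 3 sets an outer limit: "Only participants who are enrolled at Baseline (complete the T1 survey) will be included in the primary and secondary analyses". Section 3.1 then says: "All participants who completed at least one workshop will be included in intent-to-treat analyses involving workshop evaluation and workshop completion variables", and refers by number to 4.1.1 (the ISSM evaluation score) and 4.1.2 (workshop completion).
- **Per protocol set.** Section 3.2: "Youth who attend at least two of the four planned intervention workshops and complete T3 will comprise the per protocol population".
- **Derivation.** Appendix 1.2.1 gives the session count as "Numeric; Range = 0 to 4". Appendix 1.2.2 derives the binary outcome with the line "Else if WSATTEND_T2_1 in (0, 1) then WSCOMP_T2_1=0".
- **Non-starters are foreseen.** Protocol 6.3: "Participants who do not complete any workshop classes may still complete the T3 visit". Protocol 8.2 sets the timing of the follow-up visit for them.

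**The concern.** An attendance outcome is being restricted to people who attended. Within the 3.1 population the only way to be Not Complete is to attend exactly one session. A participant who enrols and never comes is left out instead of being counted as a failure. The result estimates completion among people who started, under an intent-to-treat label, when the stated question is whether the intervention is feasible in the people enrolled.

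The requirement of at least one workshop makes sense for the ISSM score, because someone who attended nothing cannot rate the workshops. The problem is that the same sentence carries it over to 4.1.2.

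Protocol 2.4 says the study is to lead to a manual for a large multi-site trial. Planning that trial would need the rate among those enrolled.

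**Working it through.** **1. Is the denominator set anywhere else?**

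- Section 3 is a necessary condition: nobody without a T1 survey is analysed. It does not put non-starters back into the set that 3.1 defines.
- The per protocol set cannot help. It requires at least two workshops, so everyone in it is Complete by definition and the rate there is 100%.
- Appendix 1.2.2 codes zero sessions as Not Complete. For this binary outcome that code has a use only if non-starters are analysed, so it is in tension with 3.1.
- The 0 to 4 range of the session count is not a contradiction by itself, because Appendix 1.2 gives the count a second purpose: "the number of completed workshops (1.2.1) is also defined to assess potential dose response of the workshop intervention on other outcomes".
- Protocol 6.3 and 8.2 show that non-starters are possible. They govern visit timing and do not contradict 3.1.

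Section 3.1 is therefore the operative population statement for 4.1.2.

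**2. Inputs for the size.**

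- N: up to 70 (Phase 2 SAP, 2.3) and up to 40 (Phase 3 SAP, 2.3). The maximum is used in each case.
- C, the number attending at least two sessions: not given, assumed below.
- z, the number enrolled who attend no session: not given, assumed below.

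The documents state no expected completion rate and no feasibility threshold, so there is no planned figure to reproduce.

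**3. Formulas.**

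- Rate under 3.1 = C/(N − z)
- Rate among all enrolled = C/N
- Ratio of the two = N/(N − z)

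**4. Results.** Each cell is the rate reported under 3.1. The column heading gives the rate among all enrolled.

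Phase 2, N = 70:

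| z | N/(N − z) | C = 28 (40.0%) | C = 42 (60.0%) | C = 56 (80.0%) |
|---|---|---|---|---|
| 0 | 1.000 | 40.0% | 60.0% | 80.0% |
| 1 | 70/69 = 1.014 | 28/69 = 40.6% | 42/69 = 60.9% | 56/69 = 81.2% |
| 7 (10%) | 70/63 = 1.111 | 28/63 = 44.4% | 42/63 = 66.7% | 56/63 = 88.9% |
| 14 (20%) | 70/56 = 1.250 | 28/56 = 50.0% | 42/56 = 75.0% | 56/56 = 100.0% |

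Phase 3, N = 40:

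| z | N/(N − z) | C = 16 (40.0%) | C = 24 (60.0%) | C = 32 (80.0%) |
|---|---|---|---|---|
| 0 | 1.000 | 40.0% | 60.0% | 80.0% |
| 1 | 40/39 = 1.026 | 16/39 = 41.0% | 24/39 = 61.5% | 32/39 = 82.1% |
| 4 (10%) | 40/36 = 1.111 | 16/36 = 44.4% | 24/36 = 66.7% | 32/36 = 88.9% |
| 8 (20%) | 40/32 = 1.250 | 16/32 = 50.0% | 24/32 = 75.0% | 32/32 = 100.0% |

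The 100.0% cells are a boundary case. They leave nobody attending exactly one session (70 − 14 − 56 = 0 and 40 − 8 − 32 = 0). They show the general property: if no one attends exactly one session and anyone completes, the rate under 3.1 is 100% however many enrolled participants never came.

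**The case against.** The strongest reply is that the exclusion is inferred. Section 3.1 says who is included and does not say that others are excluded. The only exclusive wording is in section 3, and it points to everyone enrolled. The appendix algorithm for this very outcome assigns a value to zero sessions. On that reading the documents are inconsistent, and they do not show which rule would be programmed. This stands in part: there is an inconsistency, and the appendix suggests the intention was to count non-starters. But 3.1 is the population definition, it names 4.1.2 explicitly, and no wider set is named for it, so an analyst who follows the plan excludes them.

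The consequence is also limited. The trial is an exploratory pilot without a power calculation, and no target or decision rule uses the rate. Section 5.3 tabulates the number completing T1, so a reader could rebuild the all-enrolled rate if the number completing the workshops is shown. All of that is true, and it bounds the seriousness. The planned primary figure would still be the conditional one.

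It can be said that completion among starters is a legitimate quantity. It is, as a supplement; it does not measure feasibility among those enrolled.

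Finally, amending 3.1 alone may not be enough. Appendix 1.2.1 sets the session count to missing when every attendance item is blank, and Appendix 1.2.2 then sets completion to missing. The documents do not say whether the tracking form is filled in for someone who never attends. This point stands and is taken up in the fix.

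**Conclusion.** The concern holds for both phases. As written, section 3.1 makes the primary feasibility rate conditional on having started, and neither section 3 nor the per protocol set corrects it. The rate is inflated by the factor N/(N − z) whenever at least one enrolled participant attends nothing and at least one completes. With z = 0 there is no bias.

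The size cannot be known from the documents, because they give neither z nor the number completing. Every percentage in the tables rests on assumed values and on enrolment reaching its maximum. One non-starter makes little difference (factor 1.014 or 1.026). Non-start rates of 10% and 20% give factors of 1.111 and 1.250.

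This should be fixed before the analysis. No decision rule depends on the rate, but it is a primary outcome and addresses the primary objective of each phase.

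**What to change.** In section 3.1 of both SAPs, separate the two outcomes that now share a sentence:

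- Analyse workshop completion (4.1.2) in all participants enrolled at Baseline, as section 3 defines them, with zero sessions counted as Not Complete in line with Appendix 1.2.2.
- Keep the at-least-one-workshop population for the ISSM evaluation (4.1.1) only.
- If wanted, report the completion rate among starters as supplementary.

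In the same edit, align the blank-form rule in Appendix 1.2.1, so that an enrolled participant with no recorded attendance because none took place is scored as zero sessions and not as missing.

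The cost is one sentence in section 3.1 of each SAP plus that clarification. Attendance is already tracked, so no new data are needed. The reported rate becomes less favourable if anyone attends no session.

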3.2. Per Protocol Population

Youth who attend at least two of the four planned intervention workshops and complete T3 will comprise the per protocol population. This population will form the basis for both the primary and secondary supportive analyses of the efficacy and safety endpoints.

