4.1. Primary Outcomes

4.1.1. Information Systems Success Model Score (T2)

The Information Systems Success Model (ISSM) will be used to assess for intervention acceptability and satisfaction. The 21-item scale measures four sub-domains: information quality, handbook quality, perceived usefulness, and overall satisfaction. Every item is scored on a 1 to 5 scale, with 1 being “Strongly Disagree” and 5 being “Strongly Agree”. Responses are averaged within each sub-domain to produce four sub-domain scores. The four sub-domain scores are then averaged to produce an overall ISSM score (range: 1 to 5; higher scores indicate higher acceptability/satisfaction). This scale has been adapted from Horvath et al.¹

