5.4. Analysis of Primary Outcomes

Primary outcomes for analyses include Information Systems Success Model score, workshop completion, change in Job-Seeking Self Efficacy Scale score, Protean Career Attitudes Scale score, change in Self-Directed Attitudes Scale score, and change in Values-Driven Attitudes Scale score. Details about these outcomes are described in Section 4.1.

Univariate analyses will be performed as described in Section 5.1. To the extent that data allows, multivariable analyses will adjust for sociodemographic characteristics, workshop attendance, baseline employment status, and study completeness. Analytical models will include linear regression or generalized linear models for continuous outcomes and logistic regression for binary and categorical outcomes.

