3.2. Per Protocol Population

Youth who attend at least two of the four planned intervention workshops and complete T3 will comprise the per protocol population. This population will form the basis for both the primary and secondary analyses of the efficacy and safety endpoints.

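### The single per protocol set requires T3 even for the acceptability score rated at T2, so it conditions that score on a later visit and drops valid ratings

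*SAP*

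**What the plan says.** Section 3.2 is identical in the two SAPs on membership: "Youth who attend at least two of the four planned intervention workshops and complete T3 will comprise the per protocol population". No outcome is exempted, and section 5.3 of each SAP plans to report one per protocol count.

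The role of the set differs between phases. Phase 2: "This population will form the basis for both the primary and secondary supportive analyses of the efficacy and safety endpoints". Phase 3: "This population will form the basis for both the primary and secondary analyses of the efficacy and safety endpoints". The Phase 3 sentence omits the word *supportive* and matches, word for word, the sentence that closes section 3.1 (Intent-to-Treat Population).

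Section 3.1 does separate by outcome. It requires T3 for the T1-to-T3 change variables, but for the T2 outcomes it asks only for attendance: "All participants who completed at least one workshop will be included in intent-to-treat analyses involving workshop evaluation and workshop completion variables", with a pointer to 4.1.1 and 4.1.2.

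On the outcome, section 4.1.1 states: "The Information Systems Success Model (ISSM) will be used to assess for intervention acceptability and satisfaction". Section 5.4 puts it first: "Primary outcomes for analyses include Information Systems Success Model score, workshop completion, change in Job-Seeking Self Efficacy Scale score". Section 5.4 names no analysis set. T2 falls 0–2 weeks after the workshops (Protocol 6.4). T3 falls 8 months (± 4 weeks) after the intervention in Phase 2 and 3 months (± 2 weeks) after it in Phase 3 (Protocol 6.5).

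**The concern.** A per protocol set for an acceptability rating should describe people who received enough of the programme to judge it and who gave a rating. Missing a visit months later is not a departure from anything the ISSM measures. As written, someone who attended all four sessions and completed the T2 evaluation is excluded from per protocol acceptability solely because of an event after the rating.

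There are two consequences. Ratings already in the database are left out, which costs precision whatever the reason for missing T3. And if return at T3 is related to how the workshops were rated, the per protocol mean is a mean among those who stayed, and it can differ from the mean among all adequately exposed raters. Feasibility and acceptability are the stated primary objective of each phase (SAP 1.1), so a per protocol result that agrees with the intent-to-treat one could be read as confirmation when selection may have contributed.

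**Working it through.** **The plan's own figure.** Phase 2 SAP 2.3 aims for up to 70 enrolled, "with at least 50 of these participants completing the study (~70% retention rate"). 50/70 = 71.4%, and 0.70 × 70 = 49, so 50 agrees with the rounded rate. The target allows at most 70 − 50 = 20 participants to miss T3, or 20/70 = 28.6% of those enrolled. Phase 3 SAP 2.3 gives up to 40 enrolled and no retention target.

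**Does 3.2 reach the ISSM?** Set 3.1 and 3.2 side by side. Both role sentences speak of efficacy and safety endpoints. In 3.1 that sentence directly follows text that assigns 4.1.1 and 4.1.2 to the population, so there the phrase takes in the ISSM. The natural reading of the same phrase in 3.2 takes it in too.

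**Shift in the mean.** Among raters with at least two workshops, let f be the share who miss T3 and d the mean ISSM of T3 returners minus that of non-returners. Then

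per protocol mean − mean of all such raters = f × d.

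The documents give neither f nor d. Take 70 raters with all 20 losses among them, f = 0.286:

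| d (assumed) | Shift |
|---|---|
| 0 | 0 |
| 0.5 (non-returners lower) | 0.286 × 0.5 = +0.14 |
| 1.0 (non-returners lower) | 0.286 × 1.0 = +0.29 |
| −0.5 (non-returners higher) | 0.286 × (−0.5) = −0.14 |

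The value of f is itself uncertain. Some who miss T3 may never have rated: with 10 of 70 lost (14.3%) the shift is +0.07 for d = 0.5 and +0.14 for d = 1.0. If no rater is lost it is 0. It can also exceed 28.6%: if only 50 people rate and all 20 losses fall among them, f = 40% and the shift is +0.20 for d = 0.5.

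**Precision.** With equal spread, the interval from 50 ratings is √(70/50) = 1.18 times as wide as from 70, about 18% wider. For scale, the 90% half-width at n = 50 is 1.645 × SD/√50, or 0.12 to 0.21 for an assumed SD of 0.5 to 0.9.

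**Phase 3.** Assuming 12 of 40 lost (30%), the shift is +0.15 for d = 0.5, +0.30 for d = 1.0 and −0.15 for d = −0.5. The 12 is an assumption with no basis in the SAP.

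**Workshop completion.** Section 4.1.2 defines completion as at least two of four sessions, which is also a condition of entry to the per protocol set. Completion in that set is therefore 100% by construction.

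**The case against.** The strongest reply has four parts.

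- *The ISSM may not be meant for this set.* The role sentence names efficacy and safety endpoints, SAP 2.1 lists acceptability separately from preliminary efficacy, and 5.4 assigns no set. This reading is possible, but 3.1 uses the same phrase while expressly covering 4.1.1, so it is not the natural one. If exclusion was intended, 3.2 still has to say so.
- *The main acceptability result is sound.* This stands. Section 3.1 does not require T3 for the ISSM, so the intent-to-treat result keeps the ratings of attendees who miss T3. In Phase 2 the problem is confined to a supportive analysis, and the disposition table will show the smaller count. The reply is weaker in Phase 3, where 3.2 gives the set the same role as 3.1.
- *One completer set keeps every outcome on the same people, and no ISSM threshold or hypothesis depends on it.* This is a defensible convention and limits the harm. It does not explain why 3.1 separates by outcome and 3.2 does not.
- *The direction is unknown.* This stands. A reader might infer that per protocol acceptability is likely too high, because people who disliked the programme would not come back. No passage links return at T3 to ISSM ratings. T3 is open to people who attended no workshop (Protocol 6.3) and pays $30 for the survey plus $40 for optional specimens (Protocol 8.3), which are reasons to return unrelated to the workshops. Loss could equally follow from finding work or moving.

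**Conclusion.** The point holds as a defect in the definition. Section 3.2 of both SAPs conditions a T2 rating on a visit 3 or 8 months later and drops valid ratings, out of line with the SAPs' own 3.1. It rests on reading 3.2 as including the ISSM, which the text supports but does not state outright.

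Neither the sign nor the size of a bias is established. With 70 raters and 20 lost, the shift runs from −0.14 (non-returners 0.5 higher) through 0 to +0.29 (non-returners 1.0 lower); every rating gap is an assumption, and 28.6% is the limit for all enrolled rather than an estimate for raters. The loss of about 18% in interval width under the same scenario does not depend on the direction of selection. A claim that the per protocol score is inflated, or that the main acceptability result is compromised, would go beyond the documents. The matter is more pressing in Phase 3, where the set is not labelled supportive and no retention target is given.

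**What to change.** In section 3.2 of both SAPs, make the set outcome-specific, following 3.1:

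- T1-to-T3 change outcomes: at least two workshops and T3 completed.
- ISSM and its subscales: at least two workshops and a completed T2 evaluation, with no T3 requirement.
- Workshop completion: state that it is not analysed in the per protocol set.

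In Phase 3 section 3.2, restore *supportive* so that the intent-to-treat and per protocol sets do not share the same role.

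A comparison of ISSM scores between T3 returners and non-returners, from data already held, would show whether selection matters and in which direction.

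The cost is a few sentences in each SAP and no new data. The per protocol n will differ by outcome and must be shown in the tables.
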